7.2.12. Cirrhosis Severity Grading

The severity of cirrhosis will be assessed using the Child-Turcotte-Pugh score, which reflects a composite score incorporating HE grade, extent of ascites, and bilirubin, albumin, and INR values (see [Appendix 4](#)) and MELD score calculated based on bilirubin, creatinine, and INR values (see [Appendix 5](#)).

7.3. Microbiotic-Kinetic Assessments

Feces from each voiding of the day will be collected at the pre- and postdose time points specified in [Table 3](#) for analysis of SYNB1020 transit through the GI tract. In Part 1, the 24-hour fecal sample will be weighed, homogenized, and a sample analyzed for SYNB1020 by qPCR. In Part 2, a fecal sample from the first void of the day will be collected using a collection kit. For full details on sample collection and preparation for shipment, refer to the study-specific laboratory manual.

7.4. Pharmacodynamic Assessments

In addition to the analyses specified in the following sections, serum, plasma, urine, and feces will be collected and stored for exploratory analyses, which may include, but are not limited to, microbiome analyses, fecal arginine measurements, and an ex vivo fecal ammonia consumption studies. For full details on sample collection, refer to the study-specific laboratory manual. A single blood sample may be collected at pre-screening. Urine and blood samples will be collected at screening and at the pre- and postdose time points specified in [Table 3](#). The following laboratory measurements will be performed to evaluate the preliminary pharmacodynamics of SYNB1020:

- Plasma ammonia (morning fasting and 24-hour profile to calculate AUC)
 - Samples for venous ammonia will be drawn relative to meal times (breakfast, lunch, and dinner) according to the following schedule. Following an overnight fast, subjects will have a baseline sample drawn for ammonia at 0 hours (before breakfast) and will be given a high-protein shake for breakfast, followed by IP administration on dosing days. Subsequently, samples for venous ammonia will be drawn on:
 - Day -2: +2 hours, +4 hours (before lunch), +6 hours, +9 hours (before dinner), +11 hours, +14 hours, +18 hours, and +24 hours (before breakfast on Day -1).
 - Day 5: +2 hours, +3 hours, +4 hours (before lunch), +5 hours, +6 hours, +9 hours (before dinner), +11 hours, +14 hours, +18 hours, and +24 hours (before breakfast on Day 6).
 - Day 6: +2 hours, +4 hours (before lunch), +6 hours, +9 hours (before dinner), +11 hours, +14 hours, +18 hours, and +24 hours (before breakfast on Day 7).

[REDACTED]

[REDACTED]

[REDACTED]

[REDACTED]

- Bristol stool form scale (BSFS) for each bowel movement²²

[REDACTED]

7.5. Follow-up Assessments

7.5.1. End-of-study/Discharge Visit

At least 12 hours after completion of the dosing period (i.e., on Day 7 for subjects who continue IP dosing per protocol), an EOS/Discharge visit will be performed. For subjects who discontinue study dosing prematurely, the EOS/Discharge Visit should be completed within 24 hours of discontinuation, and every effort should be made to perform the procedures specified in (Table 3).

7.5.2. Follow-up After Completion of Study Dosing

One week (7 ± 1 days) after discharge from the inpatient unit, subjects will return for clinical evaluation and bring a 1-week post-dose fecal sample. Subjects will be provided diary cards for collection of AE data. Feces will continue to be collected weekly for the first 6 weeks following discharge and biweekly until a subject has a negative SYNB1020 fecal test for up to 10 weeks following completion of study dosing. Subjects who remain colonized with SYNB1020 after 10 weeks following the last dose will be treated with a 3-day course of oral ciprofloxacin. Subjects who are allergic to ciprofloxacin can be treated with antibiotics based on reported sensitivity at the investigator's discretion. Refer to the SYNB1020 Investigator's Brochure for further details. A SYNB1020 fecal test will be performed 3 to 5 days following completion of antibiotic treatment solely for research purposes and will not guide subject follow-up decision making. An AE assessment will be performed by telephone at least 7 days after completion of antibiotic treatment. If no AEs are reported, subjects will not require any further follow-up and will be considered to have completed the study requirements. If AEs are reported, subjects will be advised to return to the inpatient facility for a comprehensive physical examination, laboratory assessment, and AE causality determination.

7.6. Sample Retention for Exploratory Analyses

Blood, urine, and fecal samples may be stored for future analyses related to metabolism and microbiome evaluations for up to 5 years. Any unused samples will be destroyed.

Table 3: Schedule of Events

Study Period	Optional Pre-Screening	Screening	Inpatient Monitoring										Follow-up ^a			
	Within 7 days of Screening		-51 to -6	-5	-4	-3	-2	-1	1	2-4	5	6	7 EOS/Discharge Visit ^b	14 Follow-up Visit	Up to 70 days after last dose	
Informed consent for pre-screening	●															
Informed consent		●														
Medical history	●	● ^c	●													
Detection of elevated portal hypertension		● ^d														
Imaging to rule out hepatocellular carcinoma		● ^d														
Physical examination		●	●									● ^e	● ^e			
FibroScan						●										
Screening for drugs of abuse (urine drug screen)		●	●													
Screening for infectious disease (HIV/Hepatitis B, C serology)		●														
Laboratory tests (CBC, LFTs, blood chemistry, urinalysis, PT/aPTT)		●				●			● ^f			●				
FSH (in females if non-childbearing potential status is equivocal based on medical history)		●														
Record concomitant medications		●	●	●	●	●	●	●	●	●	●	●	●	●		
Adverse event reporting		●	●	●	●	●	●	●	●	●	●	●	●	●		
Vital signs ^g		●	●	●	●	●	●	●	●	●	●	●	●	●		
Electrocardiogram		●				●			● ^f				●			
Fasting spot venous ammonia	●	● ^h				●			●	●	●	●	●			
Admit to inpatient facility (in the morning after an overnight fast)			●													
Required inpatient stay			●	●	●	●	●	●	●	●	●	●	●			
Subject randomization (Part 2 only)							●									
Dietary control ⁱ			●	●	●	●	●	●	●	●	●	●	●			

Study Period	Optional Pre-Screening	Screening	Inpatient Monitoring										Follow-up ^a	
			-51 to -6	-5	-4	-3	-2	-1	1	2-4	5	6	7 EOS/Discharge Visit ^b	14 Follow-up Visit
Administer H2 inhibitor (ranitidine 150 mg BID 30-60 minutes before breakfast and the evening snack) ^j			•	•	•	•	•	•	•	•	•			
Administer assigned IP (SYNB1020 or placebo, TID) with breakfast, lunch, and dinner ^k								•	•	•	•			
24-hour profile for venous ammonia ^l						•				•	•			
██						■					■			
██						■					■			
██						■					■			
██						■					■			
██						■					■			
Fecal SYNB1020 PCR ⁿ			•					•	•	•	•	•	•	•
██						■					■			
Hepatic encephalopathy grading (West Haven grade)						•					•			
Child-Turcotte-Pugh score		•				•					•			
Model for End-Stage Liver Disease score		•				•			• ^f		•			
BSFS for each bowel movement collected			•	•	•	•	•	•	•	•	•	•		
Plasma collection for exploratory analyses							•				•			
Urine collection for exploratory analyses							•				•			
Review of adverse event diary card														•

Abbreviations: aPTT = activated partial thromboplastin time; BID = twice daily; BSFS = Bristol stool form scale; CBC = complete blood count; EOS = End of Study; FSH = follicle-stimulating hormone; h = hour(s); H2 = histamine-2 receptor; HIV = human immunodeficiency virus; ██████████ IP = investigational product; LFT = liver function test; PCR = polymerase chain reaction; PPI = proton pump inhibitor; PT = prothrombin time; TID = 3 times daily; ██████████

^a One week (7± 1 days) after discharge from the inpatient unit, subjects will return for clinical evaluation and bring a 1-week post-dose fecal sample. Feces will continue to be collected weekly for the first 6 weeks following discharge and biweekly until a subject has a negative SYNB1020 fecal test for up to 10 weeks following completion of study dosing. Subjects who remain colonized with SYNB1020 after 10 weeks following the last dose will be treated as described in [Section 7.5.2](#).

^b At least 12 hours after completion of the dosing period (i.e., on Day 7 for subjects who continue IP dosing per protocol), an EOS/Discharge visit will be performed. For subjects who discontinue study dosing prematurely after having received at least one dose of SYNB1020/placebo, the EOS/Discharge Visit should be completed within 24 hours of discontinuation.

^c If not obtained during pre-screening.

^d Procedures to detect evidence of elevated portal hypertension (i.e., FibroScan to measure liver stiffness, endoscopy to determine the presence of abdominal or esophageal varices, imaging to detect splenomegaly, or ascites) and imaging to rule out hepatocellular carcinoma may be performed during screening if necessary to determine eligibility as outlined in [Section 5.2.1.3](#).

^e Symptom-driven physical examinations will be performed on Days 7 and 14.

^f Day 4 only.

^g Vital signs will be collected every 8 hours during the dosing period (Days 1 through 6).

^h Fasting venous ammonia will not be repeated at screening if measured at pre-screening.

ⁱ Meal times for breakfast, lunch, and dinner should be the same every day \pm 30 minutes, unless otherwise specified.

^j Subjects already on a PPI regimen will not be switched to ranitidine but will continue their prescribed PPI regimen for the duration of the study.

^k In Part 1, all subjects receive open-label IP. In Part 2, subjects are randomized to either SYNB1020 or placebo. IP will be administered immediately following a meal.

^l Samples for venous ammonia will be drawn relative to meal times according to [Table 4](#). Following an overnight fast, subjects will have a baseline sample drawn for ammonia at 0h (before breakfast) and will be given a high-protein shake for breakfast, followed by IP administration on dosing days. Samples for venous ammonia will be drawn at +2h, +4h (before lunch), +6h, +9h (before dinner), +11h, +14h, +18h, and +24h the following morning (before breakfast). Two additional samples will be collected on Day 5 at +3h and +5h

ⁿ One baseline fecal sample is required to be collected prior to SYNB1020 dosing (i.e., any time from Day -5 through Day 1). Feces will continue to be collected weekly for the first 6 weeks following discharge and biweekly (every other week) until a subject has a negative SYNB1020 fecal test for up to 10 weeks following completion of study dosing. Subjects who remain colonized with SYNB1020 after 10 weeks following the last dose will be treated with a 3-day course of oral ciprofloxacin, or other antibiotics. On Day 7, if no void has occurred by the time all other assessments have been completed, the subject may be discharged without a fecal sample.

Table 4: Schedule of Plasma Sampling for 24-Hour Ammonia [REDACTED]

Study Day Activity ^a	Time of Day										
	0 hours	+2 hours	+3 hours	+4 hours	+5 hours	+6 hours	+9 hours	+11 hours	+14 hours	+18 hours	+24 hours
Day -2											
Plasma draw for 24-hour ammonia	●	●		●		●	●	●	●	●	●
[REDACTED]	■	■		■		■					
Breakfast	●										
Lunch				●							
Dinner							●				
Day 5											
Plasma draw for 24-hour ammonia	●	●	●	●	●	●	●	●	●	●	●
Breakfast	●										
Give IP	●			●			●				
Lunch				●							
Dinner							●				
Day 6											
Plasma draw for 24-hour ammonia	●	●		●		●	●	●	●	●	●
[REDACTED]	■	■		■		■					
Breakfast	●										
Give IP	●			●			●				
Lunch				●							
Dinner							●				

Abbreviations: IP = investigational product

^a Plasma draws occur before meals and meals occur before IP administration, as applicable.

8. STUDY DISCONTINUATION

8.1. Sponsor Discontinuation Criteria

This study may be discontinued at any time due to safety concerns (including, but not limited to, the stopping rules described in [Section 4.3](#)), failure to meet expected enrollment goals, administrative reasons, or at the discretion of the Sponsor. Should the study be terminated prematurely, the Sponsor will provide written notification to the Investigator and regulatory authorities and will specify the reason(s) for early termination. The Investigator must inform the IRB promptly and provide the reason(s) for the termination.

8.2. Study Discontinuation for Individual Subjects

Subjects must discontinue further IP administration and withdraw from the study for the following reasons:

- Withdrawal of consent;
- Investigator decision;
- Significant noncompliance with protocol procedures;
- >1 missed dose of investigational product
- Necessity for treatment with systemic antibiotics;
- Clinically significant allergy or hypersensitivity reaction to SYNB1020;
- Development of any of the following toxicities:
 - AE of Grade 3 or greater severity according to the NCI CTCAE or life-threatening AE if not covered by CTCAE;
 - Episode of clinically overt HE (West Haven grade 2 or higher; see [Appendix 2](#))
 - QTc interval of > 520 msec or an increase from baseline of > 60 msec confirmed in a repeat test after at least 20 minute;
 - Any of the following laboratory abnormalities:
 - Grade 3 liver enzyme abnormalities and 10-fold ULN for those with normal values at baseline OR a 5-fold increase or 10-fold ULN for those with abnormal values at baseline, whichever is lower;
 - Hemoglobin levels of < 8 g/dL confirmed in a repeat test or requiring blood transfusion;
 - Platelet count of < 20,000/mL confirmed in a repeat test;
 - eGFR < 30 mL/min/1.73m² confirmed in a repeat test;
 - PT > 6.0 sec over ULN or INR level of > 2.3 confirmed in a repeat test;
 - Bilirubin > 5 × ULN confirmed in a repeat test;

- Any other laboratory abnormality of Grade 3 or great severity not covered above and not present at baseline, confirmed in a repeat test.

Subjects may withdraw their consent at any time for any reason without prejudice to their future medical care by the physician or at the institution. If a subject withdraws consent, the date and stated reason for consent withdrawal should be documented. Subject data collected up to the date of consent withdrawal will be included in the analyses.

Subjects who withdraw from the study prior to receiving SYNB1020/placebo are not required to complete the safety follow-up period. Subjects who receive at least one dose of IP and withdraw from the study are required to complete the tests and evaluations for the EOS/Discharge Visit at the time of withdrawal. Subjects who discontinue study treatment after the first administration of SYNB1020/placebo and withdraw from the study will not be allowed to enroll again at a later date. If a subject misses a dose of IP for any reason, the subject should continue with the study and take the next dose at the time specified in [Table 3](#). A subject who misses more than one dose of IP should be withdrawn from the study. If a subject who withdraws from the study has an ongoing AE, every effort will be made to follow the AE until the event has resolved, stabilized, or returned to baseline status. The Sponsor must be notified of all study withdrawals within 24 hours.

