9.2.1. Clarification of Serious Adverse Event Definition

- Death is an outcome of an SAE and not an SAE in itself. When death is an outcome, the event(s) resulting in death should be reported (e.g., “pulmonary embolism” with a fatal outcome). The appropriate diagnosis or term should be recorded and assigned severity Grade 5.
- In instances of death due ultimately to the underlying disease, the cause of death should be indicated as the specific event or condition resulting in death to the extent possible. If no appropriate term with a Grade 5 severity in the CTCAE can be identified, then a term should be selected from the CTCAE category “Death”.
- “Life-threatening” means that the subject was at immediate risk of death from the event as it occurred. This does not include an event that might have led to death if it had occurred with greater severity. Grade 4 events (e.g., thrombocytopenia) are not always serious unless they have life-threatening consequences or result in hospitalization.

- Pre-planned or elective hospitalizations including social and/or convenience situations (e.g., respite care) are excluded from SAE reporting. In addition, “admissions” under 23-hour Observation or Emergency Room visits are excluded from SAE reporting; however, such events should still be reported on the appropriate eCRF page.
- Overdose of either SYNB1020 or concomitant medication without any overdose signs or symptoms unless the event meets SAE criteria (e.g., hospitalization) are excluded from SAE reporting; however, such events should still be reported on the appropriate eCRF page.
- SAEs that occur within the safety follow-up period but are related to subsequent therapies are excluded from SAE reporting:
 - Subjects who have completed study dosing or who terminate from study and then undergo subsequent therapies during the safety follow-up period and experience an SAE specifically related to the administration of the subsequent therapy will not have those events reported as SAEs. This exclusion will include “elective” hospitalizations necessary for the administration of such therapies.

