9.4. Reporting of Adverse Events

All AEs, serious and nonserious, will be fully documented on the appropriate eCRF. For each AE, the Investigator must provide its duration (start and end dates or ongoing), intensity, assessment of causality, and whether specific action or therapy was required.

All AEs occurring from the time a subject signs informed consent through the safety follow-up period must be recorded on the eCRF. Subjects will be provided with diary cards for recording AEs during follow-up period after discharge from the inpatient unit.

All SAEs, regardless of relationship to SYNB1020/placebo, must be reported to the Sponsor within 24 hours of the Investigator's knowledge. This should be done by faxing the completed SAE Report Form to the Sponsor at the number provided on the SAE Report Form. After the final follow-up visit, only SYNB1020/placebo-related AEs/SAEs need to be collected and reported to the Sponsor, if clinically indicated.

Investigators must follow subjects with AEs/SAEs until event resolution or stabilization, withdrawal of consent, subject loss to follow-up, or death, whichever occurs first.

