4.2.9. Visit Windows

Screening procedures must be performed to determine eligibility for enrollment in both Part 1 and Part 2 within 30 days prior to admission to the inpatient facility.

During inpatient monitoring, visit windows are not a concern.

The protocol-specified visit window for the End of Study (EOS)/Discharge Visit to occur is at least 12 hours after completion of the last dose (Day 7); subjects who withdraw early should have this visit within 24 hours of discontinuation of the study drug. The first follow-up visit is specified in the protocol as occurring 7 ± 1 day after the EOS Visit, and subjects will be followed for up to 10 weeks after this first follow-up visit occurs. For continuation of follow-up visits, subjects will be required to provide weekly fecal samples (7 ± 1 day after the follow-up visit) for the first 6 weeks following discharge, and bi-weekly (14 ± 1 day) until the subject has

a negative SYNBI020 fecal test (up to 10 weeks after completion of study). However, all data will be analyzed regardless of visit windows.

Table 1 Visit Windows

Evaluation	Protocol-Specified Interval
Screening	Day -36 to Day -6
Part 1 Inpatient	Day -5 to Day 7
Part 2 Inpatient	Day -5 to Day 7
EOS/Discharge	Day 7 (12 hours post-dose)
Follow-Up	Day 13 to Day 15

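### Protocol 8.2 makes toxicity, allergy, systemic antibiotics and more than one missed dose grounds for leaving the study, not only for stopping IP, so safety follow-up of dosed early stoppers is unclear

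*Protocol*

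**What the plan says.** Protocol 8.2 applies one rule to a mixed list: "Subjects must discontinue further IP administration and withdraw from the study for the following reasons". The list contains withdrawn consent, investigator decision and significant noncompliance. It also contains more than one missed dose, need for systemic antibiotics, clinically significant allergy, and a set of toxicities (Grade 3 or worse AEs, overt HE, QTc and laboratory limits). The missed-dose rule is repeated later in the section: "A subject who misses more than one dose of IP should be withdrawn from the study". A single missed dose does not trigger it.

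For subjects who received at least one dose and then withdraw, 8.2 says that they "are required to complete the tests and evaluations for the EOS/Discharge Visit at the time of withdrawal", and that every effort will be made to follow an AE that is ongoing. Protocol 7.5.1 sets the timing: "For subjects who discontinue study dosing prematurely, the EOS/Discharge Visit should be completed within 24 hours of discontinuation".

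The same section also says: "Subjects who withdraw from the study prior to receiving SYNB1020/placebo are not required to complete the safety follow-up period". It has no matching sentence for dosed subjects.

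Protocol 7.5.2 describes the follow-up in question: a visit about one week after discharge, AE diary cards, stool testing for up to 10 weeks after dosing, and an antibiotic course for anyone still colonized at that point.

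**The concern.** Stopping a drug and leaving a trial are different decisions. Most of the 8.2 list gives good reasons to stop dosing. The toxicity, allergy, antibiotic and missed-dose items are poor reasons to stop observing someone who has swallowed a live engineered organism in a trial whose primary objective is safety and tolerability.

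Two sites could read the text differently for the same early stopper. One ends scheduled contact at the discharge evaluation. The other continues the 1-week visit, AE collection, stool testing and, if needed, eradication. Under the first reading, three things are not clearly secured: AEs that begin after discharge, the 1-week visit, and proof of clearance. The subjects concerned are those with the worst tolerability, an infection or marked toxicity, so the missing observation would be informative. They would still count in the safety population once they had a post-baseline safety assessment. SAP 4.6.1 summarises AEs by subject incidence, and SAP 4.2.8 in general makes no substitution for missing data. A subject whose observation was cut short would therefore appear as free of later events.

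**Working it through.** No design figure is at issue, so the check is mainly a comparison of text.

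**What points to leaving the study**
- Protocol 8.2: both actions are mandatory for every listed reason, and withdrawal is repeated for missed doses.
- Protocol 8.2: the only express duties for a dosed withdrawer are the discharge evaluations and follow-up of an ongoing AE.

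**What points to staying in follow-up**
- Protocol 8.2: the waiver of safety follow-up is limited to undosed withdrawers, which implies that dosed ones still owe it.
- Protocol 9.2.1: a rule on SAE reporting covers "Subjects who have completed study dosing or who terminate from study and then undergo subsequent therapies during the safety follow-up period", so a subject who has left the study can still be inside that period.
- Protocol 9.4: "Investigators must follow subjects with AEs/SAEs until event resolution or stabilization, withdrawal of consent, subject loss to follow-up, or death, whichever occurs first". Leaving the study is not among the end points listed.
- Protocol 9.3.1 (systemic antibiotics) and 9.3.2 (SBP): IP is stopped and the event is reported. Withdrawal is not mentioned. For systemic antibiotics this is the same event that 8.2 makes a reason to withdraw.
- Protocol 4.3 and SAP 2.3: if the whole study is stopped, subjects receive no more IP but stay on the follow-up schedule.
- SAP 4.2.9: for the discharge visit, "subjects who withdraw early should have this visit within 24 hours of discontinuation of the study drug". The first follow-up visit is then timed from that visit, with no exception for early withdrawers.

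No sentence says that a dosed, withdrawn subject continues under 7.5.2, and none says that the subject does not.

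**What the literal reading removes.** Take a subject who stops on Day 1.
- Planned doses: 6 days × 3 = 18. A Day 1 stop misses at least 18 − 3 = 15, so the missed-dose rule applies.
- Discharge evaluation: within 24 hours, so by Day 2.
- Follow-up runs up to 70 days after the last dose. If it ends at the discharge evaluation, at most 70 − 1 = 69 days are lost.
- This is an upper bound, because stool collection stops after a negative test. In the earlier study (SYNB1020-CP-001, Protocol 2.2.2.1) every healthy volunteer who completed had cleared within about 4 weeks, and none needed antibiotics for a positive stool test.

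**How many subjects.** In SYNB1020-CP-001, 4 of 52 (7.7%) stopped early. All four stopped with nausea and vomiting on the first dosing day, and three of them were above this trial's dose. One stopped at 5×10^11 CFU TID, arm not stated. Assume that this subject was on SYNB1020, and pool the single-day and 14-day cohorts at that dose (3 + 6 = 9 active):
- Rate: 1/9 = 11.1%, exact 95% CI 0.3% to 48.2%.
- Applied to 12 active subjects (total of 24): 12 × 0.111 = 1.3, with CI limits of 0.03 to 5.8.

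This interval excludes almost nothing. It comes from healthy volunteers and speaks only to the missed-dose route, not to antibiotics, allergy or laboratory toxicity.

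**The 30-day mortality rule (a separate matter).** Protocol 4.3 sets the trigger at 2 or more deaths in 24, or 3 or more in 40.
- A completer's last dose is on Day 6, so the 30-day point is Day 36. The last fixed visit is Day 13 to 15, which is 21 to 23 days earlier.
- One unobserved death turns 2/24 (8.3%) into 1/24 (4.2%), or 3/40 (7.5%) into 2/40 (5.0%), below the trigger.

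**The case against.** The strongest reply is that the text already implies continued follow-up. The discharge sentence in 8.2 states what is due at the time of withdrawal, not that nothing follows. Section 7.5.2 speaks of subjects without excluding early stoppers, and its eradication step is timed from the last dose. AEs are recorded through the safety follow-up period. In SYNB1020-CP-001, four subjects are described as having discontinued the study, yet 44 completed plus 8 still followed makes 52, the whole enrolment. This suggests that the sponsor used similar wording while follow-up went on, although that protocol is not available to confirm it.

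Much of this stands. A reader might infer that 8.2 waives safety follow-up, or that the trial loses these data by design. The documents do not support that: the only waiver is for undosed subjects, and 9.2.1, 9.4 and the SAP visit windows point the other way. It is also fair to say that 9.3 does not contradict 8.2 outright, since it deals with treatment and reporting and is silent on study status. What remains is that a mandatory instruction says to withdraw, and the contrary intent has to be pieced together from other sections.

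A reader might also infer that after Day 15 nothing but stool sampling remains. That is wrong. AE diary cards and AE recording continue after discharge, SAEs are reportable within 24 hours of the investigator's knowledge, and weekly stool contact could run for six weeks (Day 7 + 42 = Day 49), past Day 36. The text is unclear on whether an earlier negative test ends it.

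Finally, a reader might tie the 30-day mortality count to 8.2. It does not follow from 8.2: the absence of a dedicated contact applies equally to completers.

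**Conclusion.** The concern holds as a conflict within the plan. A stated rule in 8.2, followed literally, can end new-AE capture, the 1-week visit and stool clearance or eradication in dosed subjects who stop early, while several other sections imply that these should continue. Events already ongoing at withdrawal are covered.

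The number affected is probably small, and the documents give no useful estimate of it. The importance comes from which subjects they are and from safety being the primary objective, not from the count. The change should be made. Confidence is medium, because the conflict rests partly on implication and sites may already read the text as intended.

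The lack of a dedicated 30-day vital-status contact is real but secondary, and does not add weight to the point on 8.2.

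**What to change.** - In Protocol 8.2, make the toxicity, allergy, systemic-antibiotic and missed-dose criteria reasons to discontinue IP only. Keep withdrawn consent, and where justified investigator decision or significant noncompliance, as grounds for leaving the study.
- State in 8.2 that every dosed subject who has not withdrawn consent completes the 1-week post-discharge visit, AE collection, and stool-clearance and eradication follow-up under 7.5.2.
- Use matching wording in Protocol 9.3.

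The cost is a wording amendment and, for the few early stoppers, visits and samples that are already scheduled. No dose, eligibility criterion, endpoint or sample size changes.

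Optional and separate: add one short vital-status contact at 30 days after the last dose for every dosed subject, completers included, so that the 4.3 mortality count is secured. That is 6 + 24 = 30 contacts, or 6 + 40 = 46 at the maximum size.

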7.2.6. Clinical Laboratory Measurements

The following clinical safety laboratory tests will be performed at the time points specified in [Table 3](#): CBC with differential, prothrombin time (PT)/activated partial thromboplastin time (aPTT), serum chemistry including liver function tests (LFTs), and urinalysis. These tests will include the parameters necessary for calculation of the MELD score (i.e., serum bilirubin, serum creatinine, and INR; see [Appendix 5](#)). Screening for infectious diseases and drugs of abuse will also be performed prior to study dosing. At screening, if non-childbearing potential status is equivocal based on medical history, FSH will be assessed in selected females to confirm post-menopausal status.

Screening results will be assessed by the Investigator for inclusion of subjects in the study. Additionally, unscheduled clinical laboratory tests can be obtained at any time during the study at the Investigator's discretion. The diagnosis corresponding to any clinically significant abnormality, or abnormality requiring treatment/intervention, must be recorded as an AE.

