9.1.1. Assessment of Severity

The severity rating of an AE refers to its intensity. The severity of each AE will be categorized using the NCI CTCAE, version 4.03.²¹ For any term that is not specifically listed in the CTCAE scale, intensity should be assigned a grade of 1 through 5 using the following CTCAE guidelines:

- Grade 1: Mild; asymptomatic or mild symptoms; clinical or diagnostic observations only; intervention not indicated
- Grade 2: Moderate; minimal, local or noninvasive intervention indicated; limiting age-appropriate instrumental activities of daily living
- Grade 3: Severe or medically significant but not immediately life-threatening; hospitalization or prolongation of hospitalization indicated; disabling; limiting self-care activities of daily living
- Grade 4: Life-threatening consequences; urgent intervention indicated
- Grade 5: Death related to AE

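### Read literally, the liver-enzyme withdrawal item in Protocol Section 8.2 sets a looser mandatory limit for a normal baseline (10 × ULN or above) than for a baseline just above ULN (about 5 to 6 × ULN)

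*Protocol*

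**What the plan says.** Protocol Section 8.2 gives the reasons for which a subject must stop investigational product and withdraw. Three entries in its toxicity list matter here.

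- **The liver-enzyme item.** It reads "Grade 3 liver enzyme abnormalities and 10-fold ULN for those with normal values at baseline OR a 5-fold increase or 10-fold ULN" and closes with "for those with abnormal values at baseline, whichever is lower".
- **The catch-all laboratory item**, last in the list: "Any other laboratory abnormality of Grade 3 or great severity not covered above and not present at baseline", subject to a repeat test.
- **The AE bullet**, first in the list: "AE of Grade 3 or greater severity according to the NCI CTCAE or life-threatening AE if not covered by CTCAE".

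Investigator decision is also a listed reason. On when a laboratory result becomes an AE, Section 7.2.6 says "The diagnosis corresponding to any clinically significant abnormality, or abnormality requiring treatment/intervention, must be recorded as an AE". Section 9.6 adds that an abnormal value not already tied to an AE is recorded as one if it leads to a dosing action, if it needs intervention, or at the investigator's discretion.

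**The concern.** A mandatory limit should not be looser for the subject who starts with healthier enzymes. Here the normal-baseline half joins its two conditions with *and*, while the abnormal-baseline half joins its two with *or* and takes the lower. On that wording, a subject who rises from a normal value may stay on product at a level where a subject with a slightly raised baseline, and a smaller fold-rise, must stop.

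This is the only item in the list that names liver enzymes, and the population has cirrhosis. Sites that read the sentence differently would apply different mandatory limits. Sample size, power and type I error are not involved.

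**Working it through.** The plan states no figure to reproduce, so the check evaluates the rule directly. All values are multiples of ULN.

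**Inputs**
- Normal baseline: Grade 3 *and* 10 × ULN (Section 8.2).
- Abnormal baseline b: the lower of a 5-fold increase and 10 × ULN (Section 8.2).
- Entry limit: AST or ALT above 3 × ULN excludes (Table 2), unless the investigator judges the result not clinically significant (Part 1 inclusion item 9, Part 2 inclusion item 8).
- Grade 3 cut-off, G: not given in the documents, so left open.
- Dosing three times a day for 6 days; on-treatment laboratory tests on Days 4, 6 and 7 (SAP Section 4.6.2).

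**Step 1: literal triggers.** For a normal baseline, T = max(G, 10), so at least 10 whatever G is. For an abnormal baseline, T(b) = min(k × b, 10), with k = 5 if a 5-fold increase means 5 times baseline and k = 6 if it means a rise of 5 times baseline.

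| Baseline | Trigger, k = 5 | Trigger, k = 6 |
|---|---|---|
| 0.9 (normal) | at least 10 | at least 10 |
| 1.01 | 5.05 | 6.06 |
| 1.1 | 5.5 | 6.6 |
| 1.5 | 7.5 | 9.0 |
| 1.67 | 8.35 | 10 |
| 2 | 10 | 10 |
| 3 | 10 | 10 |

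**Step 2: inverted range.** The abnormal-baseline limit is the stricter one while k × b < 10, that is for 1 < b < 10/k. This gives 10/5 = 2 or 10/6 = 1.67. Both lie below the entry limit of 3, so such subjects can be enrolled without the investigator's override.

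**Step 3: example.** At 7 × ULN, a subject who began at 1.1 (7/1.1 = 6.4-fold) must stop on either meaning, since 7 exceeds both 5.5 and 6.6. A subject who began at 0.9 (7/0.9 = 7.8-fold) need not stop under this item.

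**Step 4: the other parse.** If the closing clause governs both halves, or *and* means *or*, the normal-baseline limit is min(G, 10). Inversion then remains only for 1 < b < min(G, 10)/k. With assumed values of G:
- G of 5 or less: none.
- G = 8: 1 to 8/5 = 1.6 (k = 5), or 1 to 8/6 = 1.33 (k = 6).
- G = 10: the full range of Step 2.

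**Step 5: do other rules close the gap?**
- The catch-all does not. It covers only other abnormalities not already dealt with, and liver enzymes are dealt with above it.
- The AE bullet acts only once the value is an AE. Under Sections 7.2.6 and 9.6 that depends on clinical significance, intervention, a dosing action or discretion. The dosing-action route is circular: the action creates the AE, so the AE cannot be what compels the action.
- If the AE bullet does reach isolated enzyme rises, the list gives two answers for a Grade 3 rise below 10 × ULN.

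**Step 6: exposure at stake.** There are 3 × 6 = 18 doses. If a Day 4 result fell in the gap and nothing else acted, the doses of Days 5 and 6 (6 of 18, 33%) would remain, or those of Days 4 to 6 (9 of 18, 50%) if the result came before dosing that day.

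**The case against.** The strongest reply is that the inversion depends on one parse. The closing clause may be meant for the whole item, in which case a normal-baseline subject stops at the lower of Grade 3 and 10 × ULN. That is plausible, and *and* is probably a slip for *or*, though the documents do not confirm it. What stands against the reply is that the sentence attaches the clause to the abnormal-baseline half, and a site has to choose between readings that give different limits.

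The second reply is that the gap is well guarded. Section 9.1.1 describes Grade 3 as "Severe or medically significant but not immediately life-threatening", so one would expect an investigator to treat a large rise from normal as a clinically significant AE. Section 7.2.6 allows that "unscheduled clinical laboratory tests can be obtained at any time during the study", and Section 9.7 has the pharmacovigilance physician and Medical Monitor review laboratory data throughout. This stands as a limit on the practical weight, but each safeguard rests on judgement, and the item exists to set a limit that does not.

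A reader might infer that the protocol lets normal-baseline subjects be dosed up to 10 × ULN, or that the sponsor chose the looser limit. The documents support neither: several other provisions can stop dosing earlier, and nothing suggests intent. A reader might also infer that a 5 × ULN cap is required. It is not shown to be, because the documents do not give the Grade 3 cut-off and contain no such enzyme limit. The bilirubin item, written as a multiple of "ULN confirmed in a repeat test", is a precedent for the form only, not for the value.

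**Conclusion.** The point holds as a minor wording defect in a mandatory safety limit. The literal inversion, at least 10 against about 5 to 6 × ULN for a baseline just above ULN, follows from the text alone and needs no outside grading table. That *and* is a slip is an inference. How much inversion would remain under the kinder reading depends on the Grade 3 cut-off, which is unknown here.

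Practical reach is small. Dosing is six inpatient days with few scheduled tests, and harm would need a normal baseline, a value in the gap, the literal reading, and no action under any other provision. The documents report no enzyme signal: no clinical-pathology effect of the related strain in primates (Section 2.2.1.3.1), and mainly mild to moderate gastrointestinal events in the Phase 1 study (Section 2.2.2.1).

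**What to change.** Reword the item: *Normal baseline: Grade 3 or 10 × ULN, whichever is lower. Abnormal baseline: 5 times the baseline value or 10 × ULN, whichever is lower.* This also settles the meaning of a 5-fold increase as 5 times baseline, which the sponsor should confirm. State whether the Grade 3 AE bullet applies to isolated enzyme elevations.

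The sponsor should check that the Grade 3 cut-off is not above 5 × ULN. If it is, an explicit normal-baseline cap of 5 × ULN, confirmed by the sponsor's medical staff, would remove what remains of the inversion: 5 × b exceeds 5 for every b above 1.

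The cost is one or two sentences in an amendment or site clarification, with no new tests or visits. A normal-baseline subject with a large rise may be withdrawn earlier and lose the Day 5 and Day 6 AUCs that SAP Section 4.7.1 requires. One such subject is 1/10 = 10% of an arm at the SAP total of 20, 1/12 = 8.3% at the protocol's 24, and 1/20 = 5% at 40.
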